6.2.3 Follow-up period and trial completion

The EOT visit will be performed at least 1 week after the last trial drug administration within the time span defined in the [Flow Chart](#).

For AE assessment, laboratory tests, recording of ECG and vital signs, and physical examination during the follow-up period, see Sections [5.2.2](#) to [5.2.5](#).

Subjects who discontinue treatment before the end of the planned treatment period should undergo the EoTrial Visit.

All abnormal values (including laboratory parameters) that are assessed as clinically relevant by the investigator will be monitored using the appropriate tests until a return to a medically acceptable level is achieved. (S)AEs persisting after a subject's EoTrial Visit must be followed until they have resolved, have been sufficiently characterised, or no further information can be obtained.

7 STATISTICAL METHODS AND DETERMINATION OF SAMPLE SIZE

7.1 STATISTICAL DESIGN – MODEL

The main objective of this trial is to establish the bioequivalence of TPA-05 compared with TPA-02 following intravenous administration of 0.2 mg/kg body weight on the basis of the primary and secondary pharmacokinetic endpoints, as listed in Section [2.1.2](#) and [2.1.3](#). The trial is designed to allow intra-subject comparisons and will be evaluated statistically by use of a linear model for logarithmically transformed PK endpoints.

Part A of this trial has been terminated after 12 subjects due to procoagulant effects that interfered also with alteplase analytics (see [1.2.5](#)). The PK-data could not be used for hypothesis testing and hence the data was only analysed descriptively.

After implementation of measures to mitigate the risk of thromboembolic complications and to avoid methodological problems with alteplase analytics Part B will be performed following a 2-stage design.

The establishment of bioequivalence will be only based on data of Part B (stage 1 and 2).

The study flow will in principle follow the adaptive sample size re-estimation (SSR) algorithm provided in [\[R19-3175\]](#) based on the standard inverse normal combination test. An outline including further details of this algorithm is provided below.

7.2 NULL AND ALTERNATIVE HYPOTHESES

Part A: no formal hypothesis will be tested. The same statistical analyses as for Part B will be performed but p-values and confidence intervals will be only considered descriptively.

Part B (stage 1 and stage 2):

The study design is an adaptive two-stage group sequential design according to [\[R14-1197\]](#) and [\[R19-3175\]](#).

Primary and secondary endpoints

For each stage, the following hypotheses are considered:

Null hypothesis H_0 (Inequivalence): $\mu_T - \mu_R \leq -\delta$ or $\mu_T - \mu_R \geq \delta$

where μ_T and μ_R are the means of the log-transformed endpoint for the test and reference treatments, respectively, and δ is the bioequivalence limit that defines the acceptance range on the logarithmic scale. Alternative hypothesis H_a (Equivalence): $-\delta < \mu_T - \mu_R < \delta$

In this trial, the bioequivalence limit δ is $\ln(1.25)$. By back-transforming (exponentiation), this translates to an acceptance range of 80.00 to 125.00% for the ratio of the geometric means (test/reference) for endpoints on the original scale.

Proprietary confidential information © 2021 Boehringer Ingelheim International GmbH or one or more of its affiliated companies

Although there are multiple primary endpoints, an alpha adjustment with respect to multiple endpoints is not needed because it is required that all primary and secondary endpoints are significant (either at interim or at the final stage, see Section 7.3). The alpha level for the significance testing will be adjusted for considering multiple stages (i.e. looks). The standard inverse normal combination test as described in [R19-3175] with pre-specified weights of \sqrt{w} and $\sqrt{1-w}$ for stage 1 and stage 2, respectively, will be used. The alpha spent for the first stage is fixed to 0.03585 (one-sided) and a user-defined alpha spending function [R10-2517] will be used such that the full level of 0.05 is spent at the final analysis. The information fraction w will be calculated as $w = 0.8 \cdot n_1^*/n_1$, where $n_1 = 18$ and n_1^* is the actual number of subjects contributing at least one evaluable PK parameter for at least one study period (i.e. are in the PKS, see Section 7.3) at the time of the interim analysis. Thus, the ratio n_1^*/n_1 accounts for example for subjects that drop-out early or do not provide evaluable PK parameters for any of the periods. It is expected that $n_1^* = n_1$ and therefore the planning values are $w = 0.8$ and $\alpha_1 = \alpha_2 = 0.03585$; these alpha values correspond to Pocock boundaries. For illustration purposes the following table provides examples on how the adjusted alpha value α_2 and the critical value (see below) will look like depending on different values of n_1^* .

Table 7.2: 1 Information fraction, adjusted alpha level and critical value for stage two depending on different values of n_1^* .

n_1^*	w	α_2	c_2
17	0.75556	0.03359	1.83050
16	0.71111	0.03159	1.85797
15	0.66667	0.02980	1.88381

At the interim analysis an assessment for BE will be performed. Thus, at the interim analysis the p-values p_{1j} based on stage 1 data, where $j = 1, 2$ denotes the index of the two one-sided tests will be compared to the value 0.03585. This is equivalent to comparing the repeated confidence interval with the boundaries 80.00% to 125.00%. If the study continues to the second stage, let p_{2j} denote the two p-values of the second stage, $j = 1, 2$. Note that p_{2j} are obtained using only the data from stage 2. BE is concluded (i.e. the null hypothesis is rejected) after the second stage if the combination of the p-values p_{1j} and p_{2j} ($j=1, 2$) is greater than the critical boundary c_2 for the final assessment, cf. [R14-1197] and [R19-3175]:

$$\sqrt{w}\Phi^{-1}(1 - p_{1j}) + \sqrt{1-w}\Phi^{-1}(1 - p_{2j}) \geq c_2,$$

where $j = 1, 2$ and j again refers to the j -th hypothesis of the TOST procedure and Φ refers to the cumulative distribution function of the standard normal distribution. Note that based on the elaborations above this results in planning values of $c_2 = 1.80107$, the critical value possibly being adapted according to the alpha spending function described above.

7.3 PLANNED ANALYSES

The analyses for endpoint apply for both study parts Part A and Part B. However, since the data of Part A could not be used for a formal statistical assessment all analyses in Part A are only considered to be descriptive.

The data from Part A will be analyses separately and will not contribute to the bioequivalence assessment.

Analysis sets

Statistical analyses will be based on the following analysis sets:

Part A:

- Treated set - part A (TS-A): The treated set includes all subjects who were randomized and treated with at least one dose of study drug. The treated set will be used for safety analyses.
- Pharmacokinetic parameter analysis set - part A (PKS-A): This set includes all subjects in the treated set - part A (TS-A) who provide at least one PK endpoint that was defined as primary or secondary and was not excluded due to a protocol violation relevant to the evaluation of PK or due to PK non-evaluability (as specified in the following subsection 'Pharmacokinetics'). Thus, a subject will be included in the PKS, even if he/she contributes only one PK parameter value for one period to the statistical assessment. Descriptive and model based analyses of PK parameters will be based on the PKS.

Part B (stage I and II):

- Treated set - part B (TS-B): The treated set includes all subjects who were randomized and treated with at least one dose of study drug. The treated set will be used for safety analyses.
- Pharmacokinetic parameter analysis set - part B(PKS-B): This set includes all subjects in the treated set - part B (TS-B) who provide at least one PK endpoint that was defined as primary or secondary and was not excluded due to a protocol violation relevant to the evaluation of PK or due to PK non-evaluability (as specified in the following subsection 'Pharmacokinetics'). Thus, a subject will be included in the PKS, even if he/she contributes only one PK parameter value for one period to the statistical assessment. Descriptive and model based analyses of PK parameters will be based on the PKS.

Adherence to the protocol will be assessed by the trial team. Important protocol deviation (IPD) categories will be described in the IQRMP, IPDs will be identified no later than in the Report Planning Meeting, and the IPD categories will be updated as needed.

Pharmacokinetics

The pharmacokinetic parameters listed in Section 2 will be calculated according to the relevant BI internal procedures. .

Individual endogenous TPA will be determined for each period as a mean of two measurements at baseline. Individual baseline levels will then be subtracted from all

Proprietary confidential information © 2021 Boehringer Ingelheim International GmbH or one or more of its affiliated companies

concentration measurements in that treatment period. In case the resulting concentration value is negative, it will be set to zero.

Plasma concentration data and parameters of a subject will be included in the statistical pharmacokinetic (PK) analyses if they are not flagged for exclusion due to a protocol violation relevant to the evaluation of PK (to be decided no later than in the Report Planning Meeting) or due to PK non-evaluability (as revealed during data analysis, based on the criteria specified below). Exclusion of a subject's data will be documented in the CTR.

Relevant protocol violations may be

- Incorrect trial medication taken, i.e. the subject received at least one dose of trial medication the subject was not assigned to
- Incorrect dose of trial medication taken
- Use of restricted medications

Plasma concentrations and/or parameters of a subject will be considered as non-evaluable, if for example

- A predose concentration (mean baseline concentration in Visit 3 corrected by the mean baseline concentration in Visit 2) is >5% C_{max} value of that subject in Visit 3
- Missing samples/concentration data at important phases of PK disposition curve

Plasma/concentration data and parameters of a subject which is flagged for exclusion will be reported with its individual values but will not be included in the statistical analyses.

Descriptive and inferential statistics of PK parameters will be based on the PKS.

Only concentration values within the validated concentration range and actual sampling times will be used for the calculation of pharmacokinetic parameters. Concentrations used in the pharmacokinetic calculations will be in the same format provided in the bioanalytical report, (that is, to the same number of decimal places provided in the bioanalytical report).

7.3.1 Primary endpoint analyses

Primary analysis

The statistical model used for the analysis of the primary endpoints for each stage of the trial will be an analysis of variance (ANOVA) model on the logarithmic scale. That is, the PK endpoints will be log-transformed (natural logarithm) prior to fitting the ANOVA model. This model will include effects accounting for the following sources of variation: sequence, subjects within sequences, period and treatment. All effects will be considered as fixed. The model is described by the following equation:

$$y_{ijkm} = \mu + \zeta_i + s_{im} + \pi_j + \tau_k + e_{ijkm}, \text{ where}$$

y_{ijkm} = logarithm of response measured on subject m in sequence i receiving treatment k in period j,

μ = the overall mean,

Proprietary confidential information © 2021 Boehringer Ingelheim International GmbH or one or more of its affiliated companies

ζ_i = the i^{th} sequence effect, $i = 1, 2$,

s_{im} = the effect associated with the m^{th} subject in the i^{th} sequence,
 $m = 1, 2, \dots, n_i$

π_j = the j^{th} period effect, $j = 1, 2$,

[figure not shown]
τ_k = the k^{th} treatment effect, $k = 1, 2$,

e_{ijkm} = the random error associated with the m^{th} subject in sequence i who received treatment k in period j .

where $e_{ijkm} \sim N(0, \sigma_W^2)$ i.i.d. Note that each stage will be analyzed separately based on data from only this stage, see Section [7.2](#).

Point estimates for the ratios of the geometric means (test/reference) for the primary endpoints (see Section [2.1](#)) and their two-sided confidence intervals (CIs) will be provided. At stage 1, the $(1 - 2\alpha_1) * 100\%$ confidence interval for the gMean ratio will be calculated. If the study continues to stage 2, the repeated confidence interval corresponding to the test decision will be calculated, in conjunction with the median unbiased point estimate as estimate for the final adjusted geometric mean ratio.

Bioequivalence is considered established if the confidence intervals of the geometric means for the primary endpoints are contained in the pre-defined acceptance range, see Section [7.2](#).

7.3.2 Secondary endpoint analyses

Primary analysis

The secondary endpoints (refer to Section [2.1.3](#)) will be calculated according to the relevant BI internal procedures and will be assessed statistically using the same methods as described for the primary analysis of the primary endpoints (see also Section [7.2](#)).

7.3.4 Safety analyses

Safety will be analysed based on the assessments described in Section [2.2.2.2](#). All treated subjects (TS, refer to Section [7.2](#)) will be included in the safety analysis. Safety analyses will be descriptive in nature and based on BI standards. No hypothesis testing is planned.

For all analyses, the treatment actually administered (= treatment at onset) to the subject will be used (any deviations from the randomised treatment will be discussed in the minutes of the Report Planning Meeting).

Treatments will be compared in a descriptive way. Tabulations of frequencies/proportions will be used to evaluate categorical (qualitative) data, and tabulations of descriptive statistics will be used to analyse continuous (quantitative) data.

Measurements (such as ECG, vital signs, or laboratory parameters) or AEs will be assigned to treatments (see Section [4.1](#)) based on the actual treatment at the planned time of the measurement or on the recorded time of AE onset (concept of treatment emergent AEs).

Therefore, measurements planned or AEs recorded prior to first intake of trial medication will be assigned to the screening period, those between first trial medication intake and end of REP (see Section [1.2.3](#)) will be assigned to the treatment period. Events occurring after the REP but prior to next intake or end of trial termination date will be assigned to 'follow-up'. In case of two or more treatments, the follow-up will be summarized according to the previous treatment. These assignments including the corresponding time intervals will be defined in detail in the Trial statistical analysis plan (TSAP). Note that AEs occurring after the last per protocol contact but entered before final database lock will be reported to Pharmacovigilance only and will not be captured in the trial database.

Additionally, further treatment intervals (analysing treatments) may be defined in the TSAP in order to provide summary statistics for time intervals, such as combined treatments, on-treatment totals, or periods without treatment effects (such as screening and follow-up intervals).

Adverse events will be coded using the Medical Dictionary for Regulatory Activities (MedDRA). Frequency, severity, and causal relationship of AEs will be tabulated by treatment, system organ class, and preferred term. SAEs, AESIs (see Section [5.2.6.1](#)), and other significant AEs (according to ICH E3) will be listed separately.

Previous and concomitant therapies will be presented per treatment group without consideration of time intervals and treatment periods.

Proprietary confidential information © 2021 Boehringer Ingelheim International GmbH or one or more of its affiliated companies

Laboratory data will be compared to their reference ranges. Values outside the reference range as well as values defined as possibly clinically significant will be highlighted in the listings. Additionally, differences from baseline will be evaluated.

Vital signs or other safety-relevant data will be assessed with regard to possible on-treatment changes from baseline. Relevant ECG findings will be reported as AEs.

ADA status and ADA titer will be analysed descriptively if applicable.

7.4 INTERIM ANALYSES

Part A:

The study was stopped for safety reasons and PK-data from Part A cannot be used for assessment of bioequivalence. Therefore, all analysis were only considered descriptively.

Part B

Blinded review of PK-data

After the first 2 cohorts a blinded review of PK-data will be performed. If these data indicate non-reliable concentration-time profiles (data do not reflect systemic alteplase concentrations due to methodological problems, as it has been observed in Part A), the trial will be discontinued (see [3.3.4.3](#)).

Review of biomarkers

Biomarkers (see [2.2.2.2](#)) can be assessed at any time point during the trial. After the first two cohorts a safety review meeting is planned (see [3.1](#)) to check whether an activation of coagulation could be observed.

Neither the PK review nor the biomarker review will influence the sample size planning of the study. Both, PK and biomarker review are not part of the adaptive design.

Two stage design with formal interim analysis:

After $n_1 = 18$ subjects have completed their crossover (Part B), recruitment will be stopped and an assessment for bioequivalence will be performed. Based on unblinded data from the first stage it will be evaluated whether the trial continues to stage 2 (Part B) or not. This analysis will be performed in an unblinded manner and will be conducted by the trial team. As described in Section [7.2](#), the p-values based on stage 1 (Part B) data are planned to be compared to the value 0.03585.

Equivalently, if the corresponding (adjusted) confidence intervals for the comparison of the primary and secondary endpoints are within the pre-specified boundaries 80.00% to 125.00% (original scale), the trial will be closed after stage 1 (Part B) due to proven bioequivalence. If bioequivalence is not shown for all primary and secondary endpoints, then a decision regarding continuation of the trial will be made by the Principal Investigator, the Trial Statistician, and the Clinical Trial Lead or their respective designees.

The power of the TOST procedure based on the first stage data will be calculated (using the planned treatment effect, the observed variability and the adjusted alpha level for stage 1). If this power is greater or equal to 0.9, the trial is recommended to stop for futility, cf. [\[R19-3175\]](#). Note that this futility rule is considered nonbinding. Note also that there will be no

Proprietary confidential information © 2021 Boehringer Ingelheim International GmbH or one or more of its affiliated companies

futility criterion with respect to the confidence interval of the gMean ratio after stage 1, in contrast to the proposed algorithm in [R19-3175]. Otherwise a sample size re-estimation (SSR) based on the unblinded data from the first stage will be performed and the trial continues to stage 2 (Part B).

The SSR will be based on the conditional power as described in [R19-3175], i.e. it will use the conditional error rates as well as the estimated conditional target power for the second stage. For the SSR it is planned to use the observed variability (gCV) and the observed geometric mean ratio (GMR) from the (unblinded) stage 1 data. The overall target power to declare bioequivalence at the end of the trial is planned to be 90%. Note that a specific power adjustment due to multiple endpoints will not be done [R17-0365] and the sample size recalculation, if required, will be based on observed results from primary and secondary PK parameters. The calculation will be performed for each parameter and the highest sample size will be used. Note that the minimum sample size for stage 2 is set to 4, as done and recommended in [R19-3175]. Moreover, for this study a maximum overall sample size of 72 will be considered. Therefore, the number of subjects in stage 2 will not exceed 42, even if the calculated sample size based on stage 1 data is higher than 42.

If bioequivalence is shown for one endpoint but not the other(s), only the endpoint(s) where bioequivalence has not been shown will be tested a second time at the end of the trial [R17-1639]. Note, however, that for completeness all PK parameters and corresponding confidence intervals for the comparison(s) as described in Section 7.3.1 and Section 7.3.2 will be calculated.

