3.3.4.3 Discontinuation of the trial by the sponsor

Boehringer Ingelheim reserves the right to discontinue the trial at any time for any of the following reasons:

1. Failure to meet expected enrolment goals overall or at a particular trial site
2. New toxicological findings, serious adverse events, or any safety information invalidating the earlier positive benefit-risk-assessment. More specifically, the trial will be terminated if more than 50% of the subjects have drug-related and clinically relevant adverse events of moderate or severe intensity, or if at least 1 drug-related serious adverse event is reported
3. Clinically relevant activation of coagulation as assessed at the safety review meeting (see [3.1](#))
4. Preliminary PK-data obtained from a blinded review after the first two cohorts indicate non-reliable concentration-time profiles (i.e. data do not reflect systemic alteplase concentrations due to methodological problems)
5. Violation of GCP, or the CTP impairing the appropriate conduct of the trial
6. The sponsor decides to discontinue the further development of the investigational product
7. BI is not allowed to produce alteplase furthermore (withdrawal of production licence)
8. The trial site is assessed to be not suitable by the sponsor, ethics committee or authorities
9. Infeasibility to achieve statistical objectives (e.g. based on the results of the interim analysis after stage 1, see section [7.4](#))

The trial will be regularly terminated after stage 1, if bioequivalence could be demonstrated after stage 1 based on interim analysis (see chapter [3.1](#))

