7.7 DETERMINATION OF SAMPLE SIZE

There is limited knowledge about the intra-individual variability of the primary endpoints. Previous trials in healthy volunteers (135.57 and 135.67) with TPA-02 were performed as a parallel design and reported a total variability (gCV) of 20.8% and 12%, respectively (both AUC and C_{max} had similar variability). Another trial in rabbits ([n00267264](#)) with TPA-02 and TPA-05 that has been performed as a crossover trial reported an intra-individual variability of approximately 15%. This latter trial observed a gMean ratio of about 100% for C_{max} and 109% for AUC. Therefore, in lack of further evidence it is assumed that the gMean ratio ranges between 100% and 109%.

All calculations below are based on the specifications given in Section [7.2](#). Particularly, a weight of 0.8 for the inverse normal approach, a sample size n₂ for stage 2 between 4 and 42 and usage of the observed gCV and gMean ratio are assumed. Using a sample size of n₁ = 18 subjects for the first stage, the probability to conclude bioequivalence after the first stage is 79% and the overall power to conclude bioequivalence is at least 95%, assuming an intra-individual gCV of 15% and a treatment difference of 9% (ratio scale) (Table [7.7: 1](#)). In order to investigate the sensitivity of the sample size, a range of gCVs around 15% and a range of gMean ratios around 109% are presented.

Table 7.7: 1

Power for concluding bioequivalence overall, power for concluding bioequivalence after stage 1 and average sample size (acceptance range 80-125%) based on an intra-individual geometric coefficient of variation around 15% and for expected ratios of geometric means (test/reference) around 109% in a two-stage 2x2 crossover trial (n₁ = 18)

gCV [%]	Ratio T/R [%]		
	104	109	114
10	>99; >99; 18.0	98.5; 98.2; 18.0	95.3; 79.4; 22.2
15	97.3; 95.4; 18.3	95.2; 79.0; 22.4	83.0; 48.3; 35.8
20	95.5; 77.3; 22.9	89.2; 56.1; 32.1	61.8; 31.6; 43.8

From the above table, even with such variations in assumptions the power is considered to be sufficient to meet the study objectives. The calculations were performed as described by Maurer et al. [[R19-3175](#)] using the function *power.tsd.in* of the R package Power2Stage Version 0.5.2 in R Version 3.6.1.

8 INFORMED CONSENT, TRIAL RECORDS, DATA PROTECTION, PUBLICATION POLICY, AND ADMINISTRATIVE STRUCTURE

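### Table 7.7:1 does not describe the interim algorithm in CTP 7.4 and the SAP: with the planned ratio fixed at 1.09, power in its 114% column is about 81/74/60%, not 95.3/83.0/61.8%

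*Protocol*

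**What the plan says.** Protocol section 7.4 has two interim steps that use a planned effect if an endpoint fails at stage 1.

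- **Futility check.** Stage-1 TOST power is calculated "using the planned treatment effect, the observed variability and the adjusted alpha level for stage 1". Then: "If this power is greater or equal to 0.9, the trial is recommended to stop for futility". The rule is nonbinding. The protocol also says there is no "futility criterion with respect to the confidence interval of the gMean ratio after stage 1, in contrast to the proposed algorithm" it cites.
- **Re-estimation.** Stage 2 is sized on the observed gCV and observed ratio, using conditional error rates and a conditional target power derived from an overall target of 90%.

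Section 7.4 prints no value for the planned effect. SAP section 7.4.1 repeats the futility rule, and its example call sets the planned ratio to 1.09.

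Protocol section 7.7 sizes stage 1 on gCV 15% and a 9% difference. Table 7.7:1 varies the true ratio (104, 109, 114%) and the gCV (10, 15, 20%). Each cell gives overall power, stage-1 power and average sample size; gCV 10% with ratio 114%, for example, reads "95.3; 79.4; 22.2". The section concludes that "even with such variations in assumptions the power is considered to be sufficient to meet the study objectives".

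**The concern.** A sensitivity table should hold the algorithm fixed and vary the truth. The planned effect is part of the algorithm: it enters the futility check and, through stage-1 power, the conditional target power. If it is allowed to follow the true ratio from column to column, the table describes a rule that already knows the answer. The off-plan columns are then wrong for the trial as specified, and the statement that power is sufficient rests partly on them.

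**Working it through.** **Inputs.** Protocol 7.2, 7.4 and 7.7: n1 = 18 (16 df), one-sided alpha 0.03585, w = 0.8, c2 = 1.80107, limits 80.00 to 125.00%, n2 from 4 to 42, overall target power 0.9. SAP 7.4.1: planned ratio 1.09. **Assumed**, because the documents print no formula: conditional target power = 1 − 0.1/(1 − stage-1 power), with n2 = 4 where this is not positive. All figures are for one endpoint.

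**Step 1: what drives the futility check.** With n1, alpha and planned ratio fixed, only the observed gCV can change the result. At gCV 12.68%:
- MSE = ln(1 + 0.1268²) = 0.01595
- SE = √(0.01595 × 2/18) = 0.0421
- ln(1.25/1.09) = 0.1370, and 0.1370/0.0421 = 3.25
- critical t (0.03585, 16 df) = 1.929

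The noncentral t probability is then 0.90. Power is 0.98 at gCV 10% and 0.79 at 15%. The cut-off is therefore an observed gCV of about 12.7%. With a planned ratio of 1.04 or 1.14 it would be 16.9% or 8.5%.

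**Step 2: reproduce the table.** Simulation of the two-stage design (200,000 trials per cell) with the stop followed and the planned effect set to each column's own ratio matches all nine printed cells to about 0.3 points. With the stop switched off, 10%/109% gives 99.5 (printed 98.5) and 15%/104% gives 98.8 (printed 97.3), so the table includes the stop. With 1.09 fixed, the 104% and 114% columns do not reproduce.

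**Step 3: fix the planned effect at 1.09.** True ratio 114%, overall power (%) and average N:

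| gCV | Printed | Planned effect 1.14 | 1.09 in both steps, stop followed | 1.09 in futility check only | 1.09, stop ignored |
|---|---|---|---|---|---|
| 10% | 95.3; 22.2 | 95.5; 22.4 | 81.2; 18.4 | 81.9; 18.8 | 88.8; 19.2 |
| 15% | 83.0; 35.8 | 83.3; 36.1 | 74.2; 30.8 | 78.8; 33.8 | 75.9; 31.4 |
| 20% | 61.8; 43.8 | 62.1; 44.1 | 60.0; 42.3 | 61.9; 43.8 | 60.1; 42.3 |

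A separate simulation with 300,000 trials per cell gives 81.4/73.9/59.7 for the fourth column. In the 104% column, fixing 1.09 raises 97.3 to 99.5 (gCV 15%) and 95.5 to 98.7 (gCV 20%). The 109% column is unchanged by construction.

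**Step 4: where the loss comes from.** Compare the third, fifth and fourth columns in turn.
- gCV 10%: the futility check alone takes 95.5 to 81.9 (13.6 points); the target power takes a further 0.7. At a true ratio of 114% the stop fires in 18.0% of trials, against 2.2% in the table's set-up.
- gCV 15%: the futility check takes 83.3 to 78.8 (4.5 points); the target power takes it to 74.2 (4.6 points).
- gCV 20%: the futility check takes 0.2 points and the target power 1.9.

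The target-power effect can be seen from the table's own stage-1 powers. At gCV 15%, a planned ratio of 1.14 gives 1 − 0.1/(1 − 0.483) = 0.81, while 1.09 gives 1 − 0.1/(1 − 0.790) = 0.52. Stage 2 is sized for a lower target. At gCV 20% the two values are 1 − 0.1/(1 − 0.316) = 0.85 and 1 − 0.1/(1 − 0.561) = 0.77, so the loss is smaller.

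**The case against.** The table is captioned for expected ratios, so letting the planned effect follow the column can be defended as nine separate planning scenarios. The SAP call is only one way the step may be implemented, 114% lies outside the assumed range of 100 to 109%, and the stop is nonbinding. These points limit the consequence. They do not rescue the table: its text presents the columns as sensitivity around 109%, only one planned value can be used at the interim, and the shortfall at gCV 15 and 20% remains if the stop is ignored.

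A reader might infer that the futility rule alone breaks the 114% column. Step 4 shows otherwise: only the 10% cell is mainly a futility effect.

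A reader might also infer that the criterion is defective and must be replaced, because it ignores the observed ratio. For example, at gCV 10% and observed ratio 1.18 (interval 110.7 to 125.8%) a stop is recommended, although conditional power at the observed values would be 85% with n2 = 20. The documents do not support that demand:
- Under the assumed formula n2 there would be 4, with conditional power of about 50%.
- Failing a stage that had 90% power at the planned effect is itself evidence against the planned effect.
- The team sees the ratio, the intervals and the re-estimated n2, and the sponsor may stop for "Infeasibility to achieve statistical objectives (e.g. based on the results of the interim analysis after stage 1").
- A futility criterion based on the confidence interval was openly declined.

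**Conclusion.** The point holds for the stated operating characteristics. For the algorithm in CTP 7.4 with the SAP's planned ratio, and the stop followed, the 114% column should read about 81/74/60% for power and about 18.4/30.6/42.2 for average N, instead of 95.3/83.0/61.8% and 22.2/35.8/43.8. With the stop ignored, power is about 89/76/60%. The 104% column is understated by 2 to 3 points at gCV 15 and 20%. In the printed 114% column one cell of three exceeds 90%; after correction none does.

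The planning case is sound: 95.2% at gCV 15% and ratio 109% stands, and the stop fires there in about 2% of trials. Type I error is not involved.

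The result rests on the assumed target-power formula, supported by its reproduction of the table; on n1* = 18 (the gCV cut-off is 12.3% at 17 and 11.9% at 16); and on a planned ratio of 1.09. The last matters: if the unprinted value were taken as 1.00, the cut-off would be 18.6%, the stop would fire in 17.5% of planning-case trials, and power there would be 81.7%.

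**What to change.** Before the interim analysis:

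1. Print the planned ratio, 1.09, in CTP 7.4, and say that it applies to both the futility check and the conditional target power.
2. Rerun the 104% and 114% columns of Table 7.7:1 with 1.09 fixed and only the true ratio varied, with and without the nonbinding stop. For the second version, state which conditional target applies when stage-1 power is already 0.9 or more and the trial continues; the figures above assume n2 = 4.
3. Revise the sentence in CTP 7.7 on sufficient power so that it matches the restated figures, in particular at 114%.

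As a note only: with n1* = 18 the stop recommendation depends solely on whether the observed gCV is below about 12.7%. The team should therefore also look at conditional power at the observed values before deciding. Replacing the criterion with numerical floors is optional.

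The cost is one simulation rerun and a few lines of text. Stage-1 size, alpha, weight and the cap of 42 do not change. The downside is that some stated power figures become less favourable.
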